Colonoscopy is the gold standard for detection of colonic polyps and colorectal cancer. Novel endoscopic enhancement by virtual electronic chromoendoscopy such as narrow-band imaging [NBI, Olympus, Japan], Fuji Intelligent Chromo Endoscopy [FICE, Fujifilm, Japan], i-scan [Pentax, Japan], techniques have been developed to aid endoscopists to better characterize colonic polyps and predict histology thus facilitating the adoption of the new paradigm of resect and discard i.e. the PIVI-ASGE strategy resulting in cost savings and avoidance of complications in patients. Several training modules have been developed and used in prior studies evaluating the performance of endoscopic image-enhancement technologies. Different training methods, have been evaluated and include face-to-face, interactive didactic teaching or web-based/computer-based self-learning teaching modules. The superiority of one training method over the other has not been well evaluated.

Trial Design

Multi-centre, international randomised controlled trial

Methodology

Participant Population

Participants will be consultants (gastroenterologists or surgeons) who are experienced in colonoscopy, training gastroenterologists, nurse endoscopists and junior doctors/medical students (who are naive in colonoscopy).

We aim to recruit 10-20 consultants/attending, 10-20 trainees/GI fellows, 10-20 nurse endoscopists (if applicable) and 10-20 junior doctors (non-GI trainees) from each centre. The participants will be randomised to receive self-directed computer based learning or face-to-face classroom didactic computer training module.

The above will be replicated at other centres: UK, USA, Italy, Germany and Japan.

Study duration: 2 years

Statistical Methodology

Performance characteristics of the participants for diagnosing colonic neoplastic vs. non neoplastic lesions (sensitivity, specificity, NPV, PPV and accuracy) will be calculated by comparing predicted histology with actual histology for all polyps and for those diagnosed with high confidence.. These performance characteristics between the two groups (face-to-face classroom training vs. self training module) will be compared using the Fisher's exact test. A P value of <0.05 will be considered to be statistically significant. *Kappa* statistic will be used to determine inter-observer agreement in polyp video classification during the training session.

Sample size

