Assuming a non-inferiority trial with one-sided distribution (face to face training versus computer based training), and power of 90% the sample size is 375 observations (observation=1 video scored). This falls to 271 observations if 0.80 1-beta error is set. As we will use 60 videos per participants, we would need a minimum of 7 participants in each centre. To minimise any potential errors we aim to recruit 10-20 participants from each group (as described above) from each centre.

Objectives

To assess the impact of didactic face-to-face training vs. self-directed computer based training module.

To evaluate the impact of an educational training module has on the ability of clinicians to differentiate small/diminutive polyps.

Outcome Measures

A pre-training assessment will be completed by participants. Performance at predicting histology (neoplastic vs. non-neoplastic) will be assessed using sensitivity, specificity, PPV, NPV and accuracy. The proportion of high and low confidence diagnoses will be also documented.

Following training, participants will immediately complete a post-training assessment and performances will be observed comparing with pre-training assessment. A follow up assessment at 6 months will be completed to assess the retention and sustainability of skills acquired.

Kappa inter-observer variability between the raters will be assessed.

Intervention

Training module: didactic face-to-face classroom training or computer-based self-learning training module

Trial Schema

[figure not shown]

Table of Contents

Protocol development and sign off	2
Key Protocol Contributors	2
[name]	2
[name]	2
[name].....	2
Protocol Amendments	2
CI Signature Page.....	3
Sponsor statement:.....	3
Administrative Information	5
Trial Summar	7
Title	7
Diminutive polyp training module using novel endoscopic imagin: a comparison between didactic training and self-directed computer based training	7
Trial Design	7
Objectives	7
Participant Population and Sample Size	Error! Bookmark not defined.
Outcome Measures	8
Intervention	Error! Bookmark not defined.
Trial Schema	10
Table of Contents.....	11
1. Background and Rationale.....	13
1.1. Trial Rationale	16
1.2. Justification for participant population.....	16
1.3. Justification for design	17
2. Aims, Objectives and Outcome Measures.....	17
2.1. Aims and Objectives	17
2.2. Outcome Measures.....	17
3. Trial Design and Setting	17
3.1. Trial Design.....	17
3.2. Trial Setting	17
4. Eligibility	17

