More recently Rastogi's group sought to identify which training method was more effective in prediction of diminutive polyp histology amongst trainees: didactic face to face training versus computer-based self-learning ²⁶. The participants were randomised to either receive didactic training in the form of a classroom training session or self-learning via computer-based material on characterisation of polyps using NBI. Trainees reviewed 40 videos of diminutive polyps with the histology being revealed and explained. Both groups were given a further 40 videos for testing. This study found those taught in the didactic group characterised polyps with higher confidence, but the overall performance was similar in the two groups. The accuracy and sensitivity were slightly better in the self-learning group (93.9% vs 85.7% p 0.01 and 95.0% vs 86.9%; p0.03 respectively) in those polyps assessed with high confidence. This study demonstrates that a computer-based training module can be as effective in didactic training, perhaps a reflection on the amount of online self-learning trainees are exposed to.

We aim to recruit participants to receive either didactic face-to-face training or self-directed computer based learning, whereby participants will be taught how to characterise lesions using the NICE, BASIC and SIMPLE classification. We aim to recruit trainees, novice endoscopists and experienced endoscopists to compare the different groups. Pre- and post-training assessments will be completed allowing us to examine the impact of training, which will consist of 40-60 videos (equal proportion of NBI, iScan OE and BLI) in the pre-training assessment and 40-60 videos (different set of videos but also equal proportion of NBI, iScan OE and BLI) in the post-training assessment. A follow up assessment will be completed at 6 months to assess the retention of skills and sustainability of colonic polyp characterisation using the optical diagnosis techniques. An existing library of NBI and OE-iScan videos will be used and further videos will be collected during routine colonoscopies with patients consenting for images to be used for teaching purposes.

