5.3. Randomisation

Participants will be randomised into either didactic face-to-face training or computer self-training module. This will take place prior to the training event and participants will be informed of which group they have been allocated on the day by using a computerized stratified randomisation sequence where a computer-generated random number will be assigned to each participant and then randomized to each arm to ensure a balanced number in both groups.

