6.2. Schedule of Assessments

Participants who agree to take part in the study will complete a pre-training assessment prior to the training day. Assessment material will be uploaded on REDCap, hosted via the University of Birmingham. Each participant will receive a link via email to complete the assessments. Each participant will be asked to assess: Quality of video High/Low, NICE classification, SIMPLE classification, BASIC classification, High/Low confidence and Hazewinkel criteria for each video. This will be completed at least 2 weeks prior to the training day. On the training day participants will receive either didactic face-to-face feedback training or computer-based training (identical). A post-training assessment will be completed within 72 hours of training (same videos as pre-training but in a different randomised order). The website will self-populate the data in Microsoft Excel documents. Participants will then be invited to complete a final assessment at 3-4 months, which will conclude the study.

7. Data Handling and Record Keeping

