9.1. Statistical Analysis

Performance characteristics of the participants for diagnosing colonic neoplastic vs. non neoplastic lesions (sensitivity, specificity, NPV, PPV and accuracy) will be calculated by comparing predicted histology with actual histology for all polyps and for those diagnosed with high confidence.. These performance characteristics between the two groups (face to face classroom training vs. self-training module)will be compared using the Fisher's exact test. A P value of <0.05 will be considered to be statistically significant. *Kappa* statistic will

be used to determine inter-observer agreement in polyp video classification during the training session.

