9.1.4. Power Calculations

Assuming a non-inferiority trial with one-sided distribution (face-to-face training versus computer based training), and power of 90% the sample size is 375 observations (observation=1 video scored). This falls to 271 observations if 0.80 1-beta error is set. As we will use 60 videos per participants, we would need a minimum of 7 participants in each centre. To minimise any potential errors we aim to recruit 14 participants from each centre (7 randomised to face-to-face training and 7 to the computer group).

10. Trial Organisational Structure

There is no trial steering committee needed for this teaching project, The members involved are outlined in the administrative information at the start of this protocol.

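### Fisher's exact test ignores about 60 correlated readings per randomised participant: at an assumed reader ICC of 0.01–0.05, unstratified type I error is about 12–32%, not 5%

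*Combined protocol and SAP*

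**What the plan says.** Section 5.3 makes the participant the randomised unit, "by using a computerized stratified randomisation sequence where a computer-generated random number will be assigned to each participant". It does not name the stratification factors.

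Section 9.1 says the arms' performance characteristics will be "compared using the Fisher's exact test. A P value of <0.05 will be considered to be statistically significant". Statistical Methodology in the Trial Summary repeats this ("will be compared using the Fisher's exact test"). Neither place states whether the test is one- or two-sided, or what is counted in the table.

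Section 9.1.4 describes a one-sided non-inferiority design with 90% power. It says "the sample size is 375 observations (observation=1 video scored", and at 80% power "This falls to 271 observations if 0.80 1-beta error is set". It then converts readings to people: "As we will use 60 videos per participants, we would need a minimum of 7 participants in each centre". It plans 14 per centre, 7 in each arm.

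No part of the plan mentions an ICC, a design effect, a mixed model, GEE or a participant-level summary analysis.

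The plan also conflicts on the videos. Section 1 describes the post-training assessment as a "different set of videos but also equal proportion of NBI, iScan OE and BLI", while Section 6.2 says "same videos as pre-training but in a different randomised order".

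**The concern.** Fisher's exact test assumes independent observations. Sixty calls by one reader are not independent if readers differ in skill. Section 4.1 builds such differences in by enrolling colonoscopists with more than 1000 procedures, independent nurse endoscopists, trainees and people with no colonoscopy experience.

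If the readings are pooled into a 2x2 table, the test treats chance differences in reader skill as evidence about the training method. More participants do not cure this, because the excess depends on readings per person and the ICC, not on the number of people.

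For the non-inferiority aim, the same error makes the interval for the arm difference too narrow, so non-inferiority can be declared falsely. The stated sample size carries the same assumption.

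**Working it through.** **Inputs.** Readings per participant: m = 60 (Section 9.1.4), or 40 at the lower end of the range in Section 1. The value m = 30 is illustrative, for subsets such as sensitivity, specificity or high-confidence calls. Readers per arm per centre: 7 (Section 9.1.4). Nominal level: 0.05 (Section 9.1), taken as two-sided. ICC: not given; 0 to 0.05 assumed.

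**The plan's own figures.** 375/60 = 6.25, rounded up to 7, so the design effect used is 1. The figure of 375 cannot be reproduced, because no margin, expected accuracy or alpha is stated. Its alpha can be inferred: ((z(1−α) + z(0.90)) / (z(1−α) + z(0.80)))² is 1.385 at one-sided 0.05 and 1.339 at 0.025, and 375/271 = 1.384.

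**Type I error by formula.** Design effect DE = 1 + (m − 1) × ICC. Two-sided error = 2 × [1 − Φ(1.96/√DE)]. For m = 60 and ICC 0.02, DE = 1 + 59 × 0.02 = 2.18, 1.96/√2.18 = 1.33, and the error is 18.4%.

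| ICC | DE, m=60 | Two-sided, m=60 | m=40 | m=30 | One-sided 0.05, m=60 |
|---|---|---|---|---|---|
| 0 | 1.00 | 5.0% | 5.0% | 5.0% | 5.0% |
| 0.01 | 1.59 | 12.0% | 9.6% | 8.4% | 9.6% |
| 0.02 | 2.18 | 18.4% | 14.2% | 11.9% | 13.3% |
| 0.05 | 3.95 | 32.4% | 25.4% | 21.1% | 20.4% |

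**Simulated Fisher's test, 60 readings each.**

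- Beta-binomial readers, accuracy 75% or 85%, ICC 0 / 0.01 / 0.02 / 0.05: about 4 / 10 / 16–17 / 30% with 7 per arm, and 4–5 / 11 / 18 / 31–32% with 35 per arm.
- Readers crossed with common videos, accuracy 85.7% (the didactic arm of the earlier trial in Section 1) or 89% (the pooled NBI figure there), logit reader SD 0.3 / 0.5 / 0.7 (ICC about 0.01 / 0.025 / 0.05): 7–13 / 14–23 / 24–35%, and 3–5% at SD 0. A participant-level t-test on such data stays at 4–6%.
- Same reader SDs, 32 per arm, with four balanced strata carrying 50–80% of skill variance: 5–8 / 7–14 / 9–24%. An unadjusted participant-level t-test then falls to 0–3%, so the strata belong in the model.

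**False non-inferiority.** The margin is not stated. Back-solving from 375 per arm at 85.7% gives 2.927 × √(2 × 0.857 × 0.143/375) = 0.075. With a true deficit equal to that margin and 7 readers per arm, pooled readings give 8–12 / 14–20 / 20–24% at reader SD 0.3 / 0.5 / 0.7, against a nominal 5%. Participant-level analysis gives 5–7%.

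**Sample size.** Seven readers supply 7 × 60 = 420 readings. Effective number = 420/DE. Readers needed = 375 × DE/60, rounded up. Power = Φ(2.927 × √(N/(375 × DE)) − 1.645), with N = 420 if 375 is per arm and N = 840 (14 readers) if 375 is the total.

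| ICC | 420 readings are worth | Readers for 375 | Power, 375 per arm | Power, 375 total |
|---|---|---|---|---|
| 0 | 420 | 7 | 93% | >99% |
| 0.01 | 264 | 10 | 79% | 97% |
| 0.02 | 193 | 14 | 68% | 91% |
| 0.05 | 106 | 25 | 47% | 71% |

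**The case against.** No text in the plan cures the clustering. The case on the other side concerns size and scope.

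- **Stratification.** Section 5.3 specifies stratified allocation, and the 12–32% figure is for unstratified allocation. If the strata balance experience, inflation at the lowest ICC could nearly vanish. This stands as a qualification. With the factors unnamed and absent from the analysis, though, the plan cannot claim that protection, and at the upper end most of the assumed range is still well above 5%.
- **Other choices.** Forty videos give about 10–25%, and a one-sided 0.05 test about 10–20%. Both are correct, and both are still about twice the nominal level or more.
- **Unit of the table.** Section 9.1 never says that readings are pooled. That is true, but Section 9.1.4 defines an observation as one scored video. On the alternative reading, participant scores are percentages, which a Fisher table cannot take.
- **Power.** The fall to 47–79% holds only if 375 is per arm. If it is the total, 14 readers keep 71–97%. The Trial Summary also aims for 10–20 people from each of several groups per centre, well above 14. Both points weaken the power complaint but leave the error rate untouched.
- **Non-inferiority.** The simulated rates rest on a back-solved margin, which would be about 10.6 points rather than 7.5 if 375 is the total, and Section 9.1 sets out no non-inferiority test. They are illustrative. The one-sided formula column needs no margin and shows the same direction.

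**Conclusion.** The concern holds, and it affects the trial's main comparison. The test ignores correlation among the readings of each randomised person. At an assumed reader ICC of 0.01–0.05, with 60 videos, two-sided testing and unstratified allocation, type I error is about 12–32% instead of 5%. With strata that absorb 50–80% of skill variance, it is about 5–8% at the low end and 9–24% at the high end. The exact size depends on an ICC and on strata that the documents do not give, but the error disappears only if within-reader correlation is effectively zero. The same holds for 375 observations and 7 participants. The power figures also depend on whether 375 is per arm or in total. This must be fixed before analysis.

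**What to change.** **Section 9.1 and Statistical Methodology in the Trial Summary.** Replace the Fisher sentence with an analysis that respects the participant as the randomised unit. Either of these would do:

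- ANCOVA on each participant's post-training score; or
- a logistic mixed model on readings, with random effects for participant and video.

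Adjust for pre-training score, centre and experience group. Use participant-level bootstrap intervals for PPV and NPV. Report the arm difference with a one-sided 95% bound from that model, and judge it against a non-inferiority margin, which the sponsor must state.

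**Section 5.3.** Name the strata so that they can enter the model.

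**Sections 1 and 6.2.** Reconcile whether the post-training videos are the same set or a different one before specifying the video effect.

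**Section 9.1.4 and Sample size in the Trial Summary.** State that 375 observations and 7 participants assume zero within-reader correlation, and whether 375 is per arm or in total. Restate power or effective sample size with a design effect over a stated ICC range. The ICC can be estimated from the pre-training assessment without using arm. Keep a range around it, because training may change the spread between readers.

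**Cost.** Wording changes and slightly more analysis work. Participant ID, centre, experience, readings and pre-training scores are already collected. Intervals will widen, and stated power per centre will look less favourable. If five centres of 14 are pooled, each arm has 35 × 60 = 2,100 readings, worth 2,100/DE = about 1,321, 963 and 532 at ICC 0.01, 0.02 and 0.05, so pooled power may still be adequate.

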9.1.1. Planned Randomisation Methodology

A Computer-generated randomisation system will allow us to allocate the participants into two teaching groups.

9.1.2. Planned Sub Group Analyses

Subgroup analysis will include didactic training vs. computer based self-learning. We will also compare the performance of predicting histology of NICE versus SIMPLE versus BASIC in all observations as well as only taking high confidence predictions. We will compare the inter-observer agreement between NICE, SIMPLE and BASIC.

9.1.3. Planned Final Analyses

Final analysis will take place after the initial training day and after the 6-month follow up assessment.

9.1.4. Power Calculations

Assuming a non-inferiority trial with one-sided distribution (face-to-face training versus computer based training), and power of 90% the sample size is 375 observations (observation=1 video scored). This falls to 271 observations if 0.80 1-beta error is set. As we will use 60 videos per participants, we would need a minimum of 7 participants in each centre. To minimise any potential errors we aim to recruit 14 participants from each centre (7 randomised to face-to-face training and 7 to the computer group).

10. Trial Organisational Structure

There is no trial steering committee needed for this teaching project, The members involved are outlined in the administrative information at the start of this protocol.

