1.1. Trial Rationale

We hypothesise that following the training module there will be an improvement in performance between the pre-training and post-training assessments. We also hypothesise that there will be no difference between the didactic face-to-face group and the self-training group.

This is an important study as better characterisation of small polyps may eventually lead to a 'resect and discard' strategy in the future. This involves characterising small or diminutive polyps (<10mm) as either non-neoplastic or neoplastic, resecting the lesion but not sending for histopathological analysis, which has significant cost savings. In order to do this training is essential. Whilst didactic training is attractive, it is costly and resource heavy. The option of self-directed learning is an attractive one as it can be delivered at times that suit the user, at their pace and can be delivered in greater volumes.

This study is unique as it is examining the impact of the training module on different groups of participants (novice, training and experienced endoscopists), using multiple endoscopic platforms (NBI, i-Scan OE and BLI) at a multicentre, international level. It will enable us to assess whether the training module improves performance using different imaging modalities.

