2.1. Aims and Objectives

Hypothesis: performances at predicting the histology of small/diminutive polyps improves following both the didactic face-to-face feedback training and self-directed computer based training. We also hypothesise that there will no overall difference between the two teaching groups.

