2.2. Outcome Measures

Outcome measures will include accuracy of polyp prediction, sensitivity, specificity, positive predictive value and negative predictive value. Proportion of high confidence diagnoses will also be recorded. Kappa statistics will be used to determine interobserver agreement in polyp video classification.

3. Trial Design and Setting

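### Sized as a one-sided non-inferiority trial with no margin, but analysed only by Fisher's test of difference on unranked measures, so a no-difference result would not show non-inferiority

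*Combined protocol and SAP*

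**What the plan says.** The sample-size text appears twice. Section 9.1.4 opens with "Assuming a non-inferiority trial with one-sided distribution (face-to-face training versus computer based training), and power of 90" per cent, and the Sample size paragraph of the Trial Summary says the same. Both give 375 observations at 90% power and 271 at 80%, one observation being one scored video. Neither gives a margin, an expected rate, an alpha, the measure being powered, or whether 375 is per arm or in total.

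Section 9.1 says that sensitivity, specificity, NPV, PPV and accuracy, for all polyps and for high-confidence diagnoses, "will be compared using the Fisher's exact test. A P value of <0.05 will be considered to be statistically significant". The Statistical Methodology paragraph of the Trial Summary repeats this. No section describes a confidence bound set against a margin or a rule for concluding non-inferiority.

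Section 2.2 lists the measures without ranking them: "Outcome measures will include accuracy of polyp prediction, sensitivity, specificity, positive predictive value and negative predictive value". On timing, section 9.1.3 says "Final analysis will take place after the initial training day and after the 6-month follow up assessment". The expected result is given in section 1.1, "We also hypothesise that there will be no difference between the didactic face-to-face group and the self-training group", and again in section 2.1.

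**The concern.** Fisher's exact test has zero difference as its null hypothesis. A non-significant result means only that zero has not been ruled out; a deficit as large as the margin may not have been ruled out either. A non-inferiority trial takes a deficit of at least the margin as its null and concludes only when that is rejected. The 90% power therefore belongs to a test the plan never runs, and the result the authors expect cannot support the conclusion they want. Under Fisher's test, only a significant result favouring self-training would show that it is not worse.

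Section 1.1 describes face-to-face teaching as expensive and self-directed learning as easier to deliver at scale, so the useful conclusion is that self-training is not materially worse. As written, a small comparison could report no difference when self-training is worse by the whole margin. A large one could report self-training as significantly worse when the deficit is inside the margin. With no primary measure or time point, the document also does not say which result decides.

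**Working it through.** **Can 375 be reproduced?** Not from the document, because margin, rate and alpha are all absent. Some of the inputs can be inferred.

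**Alpha.** For a fixed margin and rate, n is proportional to (z(1−α) + z(power))². The stated ratio is 375/271 = 1.384.

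| One-sided α | Ratio, 90% to 80% power | 375 becomes |
|---|---|---|
| 0.025 | 1.339 | 280.1 |
| 0.05 | 1.385 | 270.7 |
| 0.10 | 1.457 | 257.3 |

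Only 0.05 returns 271.

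**Implied margin.** With equal true rates p and n per arm, margin = (1.645 + 1.282) × √(2p(1−p)/n) = 2.926 × √(2p(1−p)/n). The rates are assumptions.

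| Assumed rate | 375 per arm | 375 in total (187.5 per arm) |
|---|---|---|
| 80% | 8.55 points | 12.09 points |
| 90% | 6.41 points | 9.07 points |

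Other rate and margin pairs fit exactly: 77% with 9 points and 73% with 9.5 points both give 375 and 271 per arm. The margin cannot be recovered.

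**Number of comparisons.** 5 measures × 2 sets (all, high confidence) × 2 times = 20, if all are run at both times.

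The next three checks are illustrations and treat videos as independent.

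**One data set.** Take 319/375 (85.1%) against 304/375 (81.1%). Fisher's two-sided P is 0.17. The difference is −4.0 points and its standard error is √(0.851×0.149/375 + 0.811×0.189/375) = 2.73 points. The one-sided 95% lower bound is −4.0 − 1.645 × 2.73 = −8.5 points. The margin implied at 85% is 7.6 points, so the test shows no significant difference and non-inferiority is not shown.

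**True deficit equal to the implied margin** (exact enumeration of both binomials):

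| n per arm | Reference rate | Deficit | Fisher non-significant | One-sided 95% bound wrongly passes |
|---|---|---|---|---|
| 375 | 90% | 6.41 | 29% | about 5% |
| 375 | 80% | 8.55 | 24% | about 5% |
| 187 | 90% | 9.07 | 34% | about 5% |
| 187 | 80% | 12.09 | 27% | about 5% |

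At 375 per arm and a 90% rate, Fisher's test is non-significant in about 65% of trials with a 4-point deficit and about 35% with a 6-point deficit.

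**A larger trial.** One reading of recruitment is 5 centres × 7 participants × 60 videos = 2,100 per arm. With a 90% rate and a 3-point deficit, P<0.05 occurs in about 85% of trials. In about 82% the test is significant against self-training while the one-sided 95% bound clears a 6.4-point margin.

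**Clustering.** With 60 videos per participant, the design effect is 1 + 59 × ICC. Power at the implied margin is Φ(2.926/√DE − 1.645), and participants needed per arm are 375 × DE/60. The ICCs are assumptions.

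| ICC | DE | Power, 375 per arm | Participants per arm for 90% |
|---|---|---|---|
| 0.01 | 1.59 | 75% | 9.9, so 10 |
| 0.05 | 3.95 | 43% | 24.7, so 25 |
| 0.10 | 6.90 | 30% | 43.1, so 44 |

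**The case against.** The best counter-argument concerns size. Section 9.1.4 goes from 375 to 7 participants per centre (375/60 = 6.25) and then to 7 per arm per centre, so 375 may mean per arm within each centre. A pooled multi-centre analysis would then be much larger. At 2,100 per arm, with independent videos, Fisher's test almost never misses a deficit of 6.41 points (rate 90%) or 8.55 points (rate 80%), and it misses a 4-point deficit in only about 2% of trials. Power after clustering would be about 100%, 97% and 84% at ICCs of 0.01, 0.05 and 0.10. This stands: the 24-34% figures describe a comparison of 187 to 375 videos per arm, not every reading of the plan. It does not rescue the analysis, because at the larger size the error runs the other way.

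The implied margins do rest on assumed rates; at 95% and 375 per arm the margin is 4.7 points, still above the 3-point deficit used here. Fisher's test might be meant as one-sided, since the sidedness of P<0.05 is not stated, but it would still test zero. Section 9.1.2 lists the arm comparison among subgroup analyses but gives no method. The count of 20 is conditional, because section 9.1 ties Fisher's test to no time point.

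The document also calls this a teaching project, and the separate hypothesis of improvement after training is unaffected. Even so, the arm comparison is the title question and the first objective, and a margin chosen after results are known would carry little weight.

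**Conclusion.** The concern holds, and it must be fixed before data are seen. The plan is sized for non-inferiority and analysed for difference, with no margin and no primary measure. This follows from the text alone and needs no assumption.

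The consequences depend on rate, ICC and trial size, none of which the document settles. At 187 to 375 videos per arm, treating non-significance as equivalence would accept a margin-sized deficit roughly five to seven times as often as a proper bound (24-34% against about 5%). At 2,100 per arm the more likely error is to declare self-training worse when it lies within the margin. The inference that alpha is one-sided 0.05 is firm if the two stated sizes share the other inputs. The margin remains unknown.

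**What to change.** Amend sections 9.1 and 9.1.4 and the matching Trial Summary paragraphs:

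1. Name one primary measure at one time point. The choice is the sponsor's; post-training accuracy over all videos is one candidate. If the follow-up is chosen, first reconcile its timing (3-4 months in section 6.2, 6 months in sections 8 and 9.1.3).
2. State the reference arm, margin with justification, expected rate, alpha, and whether 375 is per arm, total or per centre.
3. For the primary measure, replace Fisher's test with a confidence bound for self-directed minus face-to-face (the direction section 1.1 suggests), allowing for clustering of videos within participant. A one-sided 95% bound matches the alpha the stated sizes imply. Conclude non-inferiority only if the bound lies above minus the margin.
4. Reword the no-difference hypothesis in sections 1.1 and 2.1 to match, and stop listing the arm comparison as a subgroup analysis in section 9.1.2.
5. Report the other measures and times as secondary estimates with confidence intervals.

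The cost is small but goes beyond wording. Data collection need not change. The sponsor must supply a margin that cannot be recovered from the document and must recheck the 90% power under clustering. The planned multi-centre recruitment may already provide the participants needed.
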